Appendix Date

Appendix F
List of Medications to be Avoided or Used with Caution in Combination
with AZD8931

	PAGE
TABLE OF CONTENTS.....	2
GUIDANCE REGARDING POTENTIAL INTERACTIONS WITH CONCOMITANT MEDICATIONS.....	3
1. DRUGS AFFECTING CYTOCHROME P450.....	3
1.1 Potent inhibitors: May increase exposure to AZD8931 by more than 3- fold.....	3
1.2 Potent Inducers of CYP3A4: May reduce exposure to AZD8931 by more than 3-fold.....	4
1.3 Moderate Inhibitors of Cytochrome P450: May increase exposure to AZD8931.....	4
2. DRUGS THAT MAY PROLONG QT INTERVAL.....	5
2.1 Drugs known to prolong QT interval.....	5
2.2 Drugs that may possibly prolong QT interval.....	6

GUIDANCE REGARDING POTENTIAL INTERACTIONS WITH CONCOMITANT MEDICATIONS

NB. This list is not exhaustive and the absence of a drug from the list does not imply that its combination with AZD8931 is safe. Please contact the Medical Monitor or AstraZeneca physician if further clarification is required.

Drugs, which are permitted at steady state on a stable dose, may be used at investigator's discretion for acute indications. (eg, ondansetron for vomiting).

1. DRUGS AFFECTING CYTOCHROME P450

1.1 Potent inhibitors: May increase exposure to AZD8931 by more than 3-fold

The following drugs should not be combined with AZD8931.

Contra-indicated		
Drug	Inhibits	Minimum washout period prior to AZD8931 administration
Ketoconazole	CYP3A4	2 days
Ritonavir	CYP3A4	
Saquinavir	CYP3A4	
Indanavir	CYP3A4	
Nefazodone	CYP3A4	
Itraconazole	CYP3A4	7 days
Clarithromycin (250 mg bd or 500 mg bd)	CYP3A4	
Erythromycin	CYP3A4	
Fluconazole 400 mg	CYP3A4	
Diltiazam	CYP3A4	2 Weeks
Quinidine	CYP2D6	7 days
Paroxetine	CYP2D6	2 weeks
Fluoxetine	CYP2D6	5 weeks

1.2 Potent Inducers of CYP3A4: May reduce exposure to AZD8931 by more than 3-fold

The following drugs should not be combined with AZD8931.

Contra-indicated	
Barbiturates	Minimum of 2 Weeks Washout prior to AZD8931 administration
Carbamazepine	
Phenytoin	
Rifampicin, Rifabutin	
St John's Wort	

1.3 Moderate Inhibitors of Cytochrome P450: May increase exposure to AZD8931

Caution should be exercised in combining the following drugs with AZD8931.

Warning of possible interaction		
Drug	Inhibits	
Verapamil	CYP3A4	These drugs are permitted but caution should be exercised and patients monitored closely for possible drug interactions. Please refer to full prescribing information for all drugs prior to co-administration with AZD8931.
Nelfinavir	CYP3A4	
Grapefruit juice	CYP3A4	Patients should abstain from eating large amounts of grapefruit and Seville oranges (and other products containing these fruits eg, grapefruit juice or marmalade) during the study. Please do not have more than a small glass of grapefruit juice (120 mL) or half a grapefruit or 1-2 teaspoons (15 g) of Seville orange marmalade daily.
Seville oranges (and other products containing Seville oranges)	CYP3A4	
Duloxetine	CYP2D6	These drugs are permitted but caution should be

Warning of possible interaction		
Drug	Inhibits	
Terbinafine	CYP2D6	exercised and patients monitored closely for possible drug interactions. Please refer to full prescribing information for all drugs prior to co-administration with AZD8931.

2. DRUGS THAT MAY PROLONG QT INTERVAL

The drugs listed in this section are taken from information provided by
and

Ref: <http://www.arizonacert.org/medical-pros/drug-lists/drug-lists.htm>

2.1 Drugs known to prolong QT interval

The following drugs are known to prolong QT interval or induce Torsades de Pointes and should not be combined with AZD8931. Recommended withdrawal periods following cessation of treatment with these agents are provided in the table.

Contraindicated drug	Withdrawal period
Clarithromycin	2 days
Droperidol	
Erythromycin	
Procainamide	
Cisapride	7days
Disopyramide	
Dofetilide	
Domperidone*	
Ibutilide	
Quinidine	
Sotalol	
Sparfloxacin	
Thioridazine	
Bepidil	

Contraindicated drug	Withdrawal period
Chlorpromazine	
Halofantrine	
Haloperidol	
Mesoridazine	
Levomethadyl	4 weeks
Methadone	
Pimozide	
Arsenic trioxide	6 weeks*
Pentamidine	8 weeks
Amiodarone	1 year
Chloroquine	

* Estimated value as pharmacokinetics of arsenic trioxide has not been studied

2.2 Drugs that may possibly prolong QT interval

The use of the following drugs is permitted (notwithstanding other exclusions and restrictions) provided the patient has been stable on therapy for the periods indicated.

Warning of possible interaction	
Drug	Minimum treatment period
Alfuzosin	2 days
Chloral hydrate	
Ciprofloxacin	
Dolasetron	
Foscarnet	
Galantamine	
Gemifloxacin	
Isradipine	
Ketoconazole	
Levofloxacin	
Mexiletine	
Nicardipine	
Octreotide	
Ofloxacin	

Warning of possible interaction	
Drug	Minimum treatment period
Ondansetron	2 days
Quetiapine	
Ranolazine	
Telithromycin	
Tizanidine	
Vardenafil	
Venlafaxine	
Ziprasidone	
Amantadine	7 days
Amitriptyline	
Amoxapine	
Clozapine	
Doxepin	
Felbamate	
Flecainide	
Fluconazole	
Fosphenytoin	
Gatifloxacin	
Granisetron	
Imipramine	
Indapamide	
Lithium	
Moexipril/HCTZ	
Moxifloxacin	
Risperidone	
Roxithromycin	
Sertraline	
Trimethoprim-Sulfa	
Trimipramine	
Voriconazole	

Warning of possible interaction	
Drug	Minimum treatment period
Azithromycin	14 days
Citalopram	
Clomipramine	
Itraconazole	
Nortriptyline	
Paroxetine	
Solifenacin	
Tacrolimus	
Fluoxetine	
Protriptyline	6 weeks
Tamoxifen	8 weeks

Amended Clinical Study Protocol: Appendix G

Drug Substance	AZD8931
Study Code	D0102C00002
Appendix Edition Number	2

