3.3.3 Exclusion criteria

Any of the following is regarded as a criterion for exclusion from the study:

1. Receipt of any of the following treatments within 4 weeks prior to study entry: chemotherapy (within 6 weeks for nitrosurea or mitomycin C), radiotherapy, hormone therapy (except for androgen-deprivation therapy for patients with prostate cancer), immunotherapy and any other anti-cancer therapies
2. Unresolved toxicity \geq CTCAE grade 2 from previous anti-cancer therapy, except alopecia
3. Prior cumulative doxorubicin dose of >360 mg/m², or the equivalent
4. History of other malignancies with the exception of basal cell carcinoma of the skin or cervical cancer in situ, within the previous 5 years
5. History of documented cardiac failure, angina pectoris requiring antianginal medication, evidence of transmural infarction on ECG, poorly controlled hypertension (systolic >180 mmHg or diastolic >100 mmHg), significant valvular disease or history of high risk dysrhythmia (such as ventricular fibrillation or ventricular tachycardia [includes ventricular triplets])
6. Resting ECG with measurable QTc interval of >460 msec at 2 or more time-points within a 24-hour time period, or history of prolonged QTc syndrome
7. Currently receiving agents designated as Class I Arizona risk for QT prolongation (see Section 3.4.6 and Appendix F). Agents designated as Class II Arizona risk for QT are allowed provided the patient has received these agents for at least 5 half-lives of the drug with no change in dose
8. The presence of any ocular disease or condition that is active or is likely to flare up during the course of the study or any systemic disease/condition that is affecting or has affected the eye in the past and may flare up, or the treatment of which may have an adverse effect on the eye. Eye conditions that are stable and of long standing, such as scars from trauma, pinguecula, atrophic pterygia etc, should not be considered as reasons to exclude the patient
9. Wearing contact lens (patients should discontinue wearing contact lens from at least 1 week prior to entering the study to 1 week following discontinuation of AZD8931)
10. Recent acute changes in patient's vision, or ongoing symptoms of ocular pain, discomfort or irritation
11. History of radiotherapy where the eye orbits was included in the treatment field

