26. Currently receiving, or recently taken, drugs (eg, prescribed and non-prescription) with known significant CYP3A4 or CYP2D6 inhibitor or inducer effects (see Section 3.4.6 and Appendix F). Where half-life data are not available, the patient should not have received the therapy within the last 4 weeks
27. Known hypersensitivity reaction or prior anaphylaxis attributed to previous therapy with oral tyrosine kinase inhibitors.
28. Current disease or condition known to interfere with absorption, distribution, metabolism or excretion of drugs
29. Personal history of repeated unexplained episodes of syncope and/or dizziness
30. If participation in the study would result in the patient donating more than 1350 mL of blood in the 12 months before the end of the study or 500 mL of blood in the 3 months before the end of the study
31. Female patients who are breast feeding, or patients of reproductive potential not employing reliable methods of birth control
32. History of use of an investigational agent within the 30 days prior to entry or who have not recovered from side effects of an investigational study drug
33. Involvement in the planning and conduct of the study (applies to both AstraZeneca staff or staff at the study site)
34. Clinical judgment by the investigator that the patient should not participate in the study

The following criterion will require exclusion from the optional **pharmacogenetic component** part of the study:

35. Receipt of a whole blood transfusion in the preceding 90 days, or a previous bone marrow transplant

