3.3.4 Restrictions

The following restrictions will apply:

1. Female patients of child bearing potential will be required to use 2 reliable methods of contraception (or abstain from heterosexual intercourse) from Screening, for the duration of the study, and for at least 28 days after the last dose of study drug. The 2 methods of reliable contraception must include 1 highly effective method (ie, intrauterine device [IUD], tubal ligation, partner's vasectomy) and 1 additional effective (barrier) method (ie, condom, diaphragm, cervical cap) or non-pharmacologic contraception measures. The female patient must be referred to a qualified provider of contraceptive methods, if needed

2. Male patients will be required to use reliable methods of contraception (condom) during any sexual contact with a female of childbearing potential for the duration of the study and until 16 weeks after the last dose of AZD8931 (even if he has undergone successful vasectomy).
3. Male patients will be advised to abstain from sperm donation from first dose until 16 weeks following receipt of the last dose of AZD8931
4. All patients will be counselled on the potential risks of foetal exposure to the study drug at the start of the study
5. No food is allowed from 2 hours before to 2 hours after taking study drug
6. Patients must not receive any concomitant anti-cancer agents or any other investigational agents while receiving AZD8931
7. Abstain from taking drugs with known significant CYP3A4 and CYP2D6 inducer/inhibitory affects (see [Appendix F](#))
8. Abstain from eating large amounts of grapefruit and Seville oranges (and other products containing these fruits, eg, grapefruit juice or marmalade) during the study. Amounts should not exceed more than a small glass of grapefruit juice (120 mL), or half a grapefruit, or 1-2 teaspoons (15 g) of Seville orange marmalade daily
9. Refrain from driving for 4 hours following ophthalmic examination if pupillary dilatation performed
10. Refrain from wearing contact lenses from at least 1 week prior to starting AZD8931 to 1 week after discontinuation of AZD8931
11. Avoid use of sun beds or tanning booths (including dye-based tanning booths) during the course of the study and for 3 months after the last dose. Use sunglasses and sun cream (with SPF minimum 15), if exposed to sunlight during this period of time

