3.3.5.4 Procedures for handling incorrect enrolled subjects

Patients not meeting the inclusion/exclusion criteria for a study should, under no circumstances, be enrolled into the study. No waivers for inclusion/exclusion criteria will be granted.

Patients who have been entered into the study in error, in violation of inclusion or exclusion criteria, will be evaluated on an individual basis to determine the likely benefits and risks to the patient if they remain in the study; such patients may remain in the study if considered appropriate by the investigator, Medical Monitor and AstraZeneca (the decision must be documented). These patients are non-evaluable for evaluation of MTD and PK and should be replaced.

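### Appendix F, Section 2.2 permits five drugs on stable therapy that Section 1.1 of the same appendix contra-indicates, and its literal wording overrides the ban

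*Protocol*

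**What the plan says.** Appendix F sorts restricted medications by mechanism. Section 1 covers drugs affecting cytochrome P450, and Section 2 covers drugs that may prolong the QT interval.

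- **Appendix F, Section 1.1** (potent inhibitors) gives its reason in the heading, "May increase exposure to AZD8931 by more than 3-fold", and its rule beneath: "The following drugs should not be combined with AZD8931". It tabulates 13 drugs with minimum washout periods.
- **Appendix F, Section 2.2** (possible QT prolongation) opens with "The use of the following drugs is permitted (notwithstanding other exclusions and restrictions"), on condition that the patient has been stable on the drug for a tabulated minimum period. It lists 55 drugs.
- **Appendix F, opening guidance** adds that drugs allowed at a stable dose may also be used for acute indications at the investigator's discretion. Its example is ondansetron.
- **Section 3.3.3, exclusion 26** excludes patients on drugs "with known significant CYP3A4 or CYP2D6 inhibitor or inducer effects". **Section 3.3.4, item 7** tells patients to "Abstain from taking drugs with known significant CYP3A4 and CYP2D6 inducer/inhibitory affects". **Section 3.4.6** bars the same class of drug during treatment. All three refer to Appendix F for the drugs concerned.
- **Section 3.3.5.4** states "No waivers for inclusion/exclusion criteria will be granted" and says of patients entered in violation of the criteria: "These patients are non-evaluable for evaluation of MTD and PK and should be replaced".

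**The concern.** One appendix gives opposite instructions for the same drugs. *Notwithstanding other exclusions* means in spite of them, so Section 2.2 as written overrides Section 1.1 for every drug on both lists. The likely intent, *subject to*, is the reverse.

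The first thing at stake is safety. A site relying on Section 2.2 could continue, or through the acute-use sentence start, a drug that the sponsor itself says may more than triple exposure, in a dose-escalation study. By comparison, Section 3.1.2 says escalation may become more conservative if exposure is only 10% to 15% above prediction.

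The second is the data. Escalation decisions rest on 3 to 6 evaluable patients per cohort, so an unrecognised interaction in one patient could produce a DLT, or distort a PK profile, that does not belong to the assigned dose.

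**Working it through.** No calculation in the plan bears on this point. The check is a comparison of lists, followed by a reading of the provisions that might settle the conflict.

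**1. Compare the lists.** Section 1.1 names 13 drugs: ketoconazole, ritonavir, saquinavir, indanavir, nefazodone, itraconazole, clarithromycin, erythromycin, fluconazole 400 mg, diltiazam, quinidine, paroxetine and fluoxetine (spelling as in the protocol). Section 2.2 names 55 distinct drugs. The 13 divide as follows:

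| Group | Drugs | Number |
|---|---|---|
| Also in Section 2.2 (permitted): conflict | ketoconazole, itraconazole, fluconazole, paroxetine, fluoxetine | 5 |
| Also in Section 2.1 (contra-indicated for QT): no conflict | clarithromycin, erythromycin, quinidine | 3 |
| Not in Section 2 | ritonavir, saquinavir, indanavir, nefazodone, diltiazam | 5 |

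5 + 3 + 5 = 13. Of the 55 drugs in Section 2.2, 55 − 5 = 50 do not conflict with Section 1.1. For fluconazole the conflict arises only at 400 mg.

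**2. Set the conditions side by side.** Merged cells are read downwards.

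| Drug | Section 1.1: minimum time off before AZD8931 | Section 2.2: minimum time on before AZD8931 |
|---|---|---|
| Ketoconazole | 2 days | 2 days |
| Itraconazole | 7 days | 14 days |
| Fluconazole | 7 days (400 mg) | 7 days (no dose given) |
| Paroxetine | 2 weeks | 14 days |
| Fluoxetine | 5 weeks | 14 days (cell uncertain in the extracted table) |

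This is the same contradiction in practical terms, not a second one. A patient cannot be both washed out of a drug and stable on it. The finding does not depend on the exact periods.

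**3. Look for a provision that settles it.**

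- Exclusion 26, restriction 7 and Section 3.4.6 prohibit significant CYP inhibitors, but they name no drug and defer to Appendix F.
- The exclusion criteria operate separately ("Any of the following is regarded as a criterion for exclusion from the study"), so passing the QT criterion does not waive the CYP criterion. This supports reading Section 2.2 as a QT-only permission. However, exclusion 7 and Section 3.4.6 also allow Class II QT agents after at least 5 half-lives at an unchanged dose, without repeating the CYP limit there.
- Nothing in the protocol ranks Section 1.1 above Section 2.2.

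**4. Trace the effect on evaluability.** Section 3.3.5.4 removes ineligible patients from the MTD and PK evaluation, but only if the violation is recognised, and Section 2.2 tells the site there is none. For drugs started on study, Section 3.4.6 says only that such patients could be considered non-evaluable and may be replaced. The replacement clause in Section 3.1.5 for confounded DLTs covers medication started during the DLT period. It does not cover a drug on which the patient was already stable, which is the situation Section 2.2 describes.

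**The case against.** The strongest reply is that the structure already resolves the conflict. Appendix F works as two filters, both of which must be passed, and a drug may properly appear under both mechanisms. Clarithromycin, erythromycin and quinidine do so. A reader sent there by exclusion 26 would go to Section 1, which is plainly headed as contra-indications. The Section 2.2 table carries its own warning of possible interaction and requires stable therapy. The literal reading also proves too much: Section 2.2 lists tamoxifen, so it would lift the bars on hormone therapy and concomitant anti-cancer agents too, which no site is likely to accept. Sites may ask the Medical Monitor or the sponsor's physician, and Sections 3.1.5 and 3.4.4 allow replacement of patients whose DLT is attributed to confounding medication.

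Much of this stands. It shows what was intended, makes misuse less likely and keeps the point minor. It does not remove the contradiction. The three drugs offered as precedent are banned in both places, so they do not show how a ban and a permission are to be reconciled. The tamoxifen example is a further reason to correct the word. The stability condition does not protect a patient already taking one of the five drugs, and the acute-use sentence relaxes it for drugs newly started. A site that reads an explicit permission has little reason to ask for clarification.

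**Conclusion.** The concern holds, as a minor inconsistency. Five of the 13 drugs contra-indicated in Appendix F, Section 1.1 are permitted in Section 2.2 by wording that overrides the ban if taken literally. The other 50 drugs in Section 2.2 do not conflict with Section 1.1.

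The main consequence is for patient safety. The only exposure figure the protocol gives for these drugs is the one in the Section 1.1 heading, more than 3-fold. How many patients might be affected cannot be derived. MTD and PK data would be affected only if a site fails to recognise a violation because of Section 2.2, or if one of these drugs is started on study and the patient is nevertheless kept as evaluable. The sample size and the escalation rule are untouched.

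The conclusion rests on the ordinary meaning of *notwithstanding* and on the absence of any precedence rule. It does not rest on an assumption that sites would misread the appendix.

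**What to change.** 1. In Appendix F, Section 2.2, replace the parenthesis with: *subject to all other exclusions and restrictions, including Sections 1.1 and 1.2*. This alone removes the override.
2. In the Section 2.2 table, delete ketoconazole, itraconazole, paroxetine and fluoxetine, or mark each as contra-indicated with a reference to Section 1.1. Mark fluconazole as not permitted at 400 mg, with the same reference. A site looking up a single drug then sees the ban where it looks.
3. As an optional clarification that follows from the first change, limit the acute-use sentence at the head of Appendix F to drugs not contra-indicated in Sections 1.1, 1.2 or 2.1.

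The cost is a wording correction to one appendix. Intended eligibility does not change, because exclusion 26 already bars significant CYP3A4 and CYP2D6 inhibitors.

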1. GENETIC COMPONENT

As an exploratory objective, it is planned to take blood samples for future pharmacogenetic analysis, with the intention to determine any potential ability to identify individuals who may respond optimally to AZD8931 or a specific dose of AZD8931, or to identify factors that may affect the absorption, distribution, metabolism or excretion or tolerability of AZD8931 or its comparators.

Optional blood samples will be collected for pharmacogenetic research. Patients who agree to take part in this genetic research will be asked to sign a separate informed consent form to confirm their willingness to have this sample taken. The patient may participate in the main study without participating in the genetic component. The samples will be stored and analysed for future research. Patients from all centres are eligible to participate in the pharmacogenetic research. No planned number of patients is required for this genetic research.

1.1 Procedures for discontinuation from genetic aspects of the study

Patients who discontinue from the study should always be asked specifically whether they are withdrawing or continuing their consent for this linked genetic research. It must be established whether the patient:

- Agrees to the genetic sample and any deoxyribonucleic acid (DNA) extracted from the sample being kept for genetic analyses in the future.
- Withdraws consent for the sample to be kept for genetic analysis in the future and wishes the sample to be destroyed. Destruction of the sample (or the DNA extracted from the sample) will only be possible so long as the particular sample is traceable. In the event that genetic research has already been performed, AstraZeneca will retain the results and associated data for regulatory reasons but these will not be used in any subsequent analyses.

The principal investigator is responsible for providing written notification to the Clinical Genotyping Group (CGG) at AstraZeneca of any patient who has withdrawn consent for the use of the sample taken for genetic research. AstraZeneca will provide written confirmation to the investigator of the actions taken with the sample, which must be filed in the investigator site file. Requests by the patient to withdraw from the genetic research should be made through the principal investigator, who will inform the CGG and the study monitor to that effect. The address of the CGG group is:

2. GENETIC MEASUREMENTS AND CO-VARIABLES

2.1 Collection of samples for genetic research

An optional blood sample for genotyping will be collected on Day 1 from patients who provide written informed consent to confirm their willingness to take part in genetic research. As genotype is a stable parameter, if for any reason the blood sample is not drawn on Day 1, it may be taken at any visit until the last study visit. The genetic blood sample should ideally be drawn through the same cannula used to draw blood samples required for the main study.

A single venous blood sample (9 mL) will be collected into a polypropylene tube containing ethylenediamine-tetra-acetic acid (EDTA) and gently inverted a minimum of 5 times to mix thoroughly. Tubes will be labelled with the protocol study number, centre number, enrolment code and date of sample collection. No personal identifiers (patient name, initials or date of birth) will be placed on the tube or accompanying documentation. A record of the date and time of the patient consent to the genetic research and the date of the blood sample collection will be recorded in the appropriate section of the case report form (CRF).

